3.11 INTERIM ANALYSIS

No formal interim analyses are planned for this study. As such, no formal statistical rule for early termination of the trial is defined. Interim study reports with descriptive analysis may be produced for regulatory or reimbursement purposes.

3.12 DOCUMENTATION AND OTHER CONSIDERATIONS

All analyses will be performed using SAS[®] for Windows, version 9.1^{5, 12} or higher.

4 VARIABLES FOR ANALYSIS

This section describes the additional variables to be presented. In general, all analyses will be summarized overall and by treatment group, unless otherwise noted in the text below or in the table mockups.

4.1 ENROLLMENT AND SUBJECT DISPOSITION

The count of subjects enrolled at each study site will be summarized. Subjects terminating from the study by 30, 180 days, and 1, 2, 3, 4 and 5 years, and the reason for early termination, will be summarized with subject counts and percentages.

4.2 DEMOGRAPHICS, SUBJECT CHARACTERISTICS, AND PROCEDURE INFORMATION

Demographic, baseline subject characteristic, and procedure information data will be summarized overall, by treatment group, and for the difference between treatment groups using descriptive statistics, as per the table mockups. The data will be summarized for each analysis population to show the balance between the treatment arms in support of the various endpoint analyses. The variables for analysis are given in each section below.

4.2.1 Demographics

- Age (in years)
- Gender at Birth

4.2.2 Risk Factors

The presence of the following risk factors:

- Current Tobacco Use
- All Diabetes Mellitus
- Non-Diabetes Mellitus
- Diabetes Mellitus Requiring Medication
- Diabetes Mellitus Requiring Insulin
- Non-medically Treated Diabetics
- Hypertension Requiring Medication
- Hypercholesterolemia Requiring Medication

4.2.3 Cardiac History

The presence of the following cardiac histories and classification of the disease:

- Prior MI
- MI within 2 Months
- History of Angina (stable angina, unstable angina)
- All Prior Cardiac Interventions
 - Prior PCI

- Prior CABG
- Prior Cardiac Intervention of Left Main

4.2.4 Physical Measurements

- Height (cm)
- Weight (kg)
- Body Mass Index (BMI) (kg/m²)
- Systolic Blood Pressure (mmHg)
- Diastolic Blood Pressure (mmHg)

4.2.5 Disease State/Severity

- SYNTAX Score
- SYNTAX Score II
- Clinical SYNTAX Score
- ACEF Score
- LVEF
- Chronic obstructive lung disease
- Peripheral vascular disease
- Prior stroke
- Modified Rankin Scale (mRS) for stroke
- Number of Diseased Vessels
- Number with ≥ 2 Diseased Vessels
- Number with \geq 3 Diseased Vessels
- Number of Vessel Treated
- Number with ≥ 3 vessels Treated
- Number with ≥ 2 vessels Treated
- Distal left main bifurcation involvement
- Chronic total occlusion present

4.2.6 Laboratory Tests

- HgbA1c
- hsCRP
- BNP
- Hgb
- WBC
- Platelets
- CK-MB
- Serum Creatinine

4.2.7 Procedure/Device Information

Procedure and device information will be summarized for the two treatment arms separately. No comparisons will be made.

4.2.7.1 **Procedure/Device Information for PCI arm only**

The following device information will be presented in a listing by-subject:

- GPIIb/IIIa Inhibitor Usage During Procedure
- Antiplatelet Usage During Procedure
- Maximum Balloon Pressure Used Over the Entire Procedure (pre-dilatation, stent deployment, post-dilatation)
- Total Number of Stents Placed
- Total Length of All Stents Placed (mm)
- IVUS and/or FFR guidance
- distal left main vs. left main ostial/body
- treatment strategies for the distal left main bifurcation
- chronic total occlusions
- bifurcation lesions

The following device information data will be summarized on a by-stent basis:

- Diameter of Stents Used (mm)
- Length of Stents Used (mm)

4.2.7.2 **Procedure Information for CABG arm only**

The following device information will be summarized in a listing by-subject:

- Total Number of grafts placed
- On pump vs. Off pump
- Single vs. bilateral ITA vs. multiple arterial graft use
- Endoscopic versus open saphenous vein harvest technique
- Epi-aortic ultrasound and/or TEE
- Prophylactic and management strategies for atrial fibrillation
- Carotid Screening

4.2.7.3 Device Malfunction

Device malfunctions and their outcomes will be listed for the PCI arm only, using subject counts.

- Device Malfunction
- Outcome of Malfunction

4.2.8 **Protocol Medications**

Antiplatelet use at discharge, 30 days, 180 days, and 1, 2, 3, 4 and 5 years summarized as:

- Number of Subjects on Clopidogrel/Ticlopidine/Prasugrel/Ticagrelor
- Duration (days) on Clopidogrel/Ticlopidine/Prasugrel/Ticagrelor
- Number of Subjects on Aspirin
- Duration (days) on Aspirin
- Number of Subjects on Dual Antiplatelet Therapy (both aspirin and Clopidogrel/Ticlopidine/Prasugrel/Ticagrelor)
- Duration (days) on Dual Antiplatelet Therapy

4.2.9 Angina Status

• Angina Status and classification at discharge, 30 days, 180 days, 6 months, and 1, 2, 3, 4 and 5 years

4.3 MORPHOLOGY AND QUANTITATIVE CORONARY ANGIOGRAPHY

Lesion morphology and quantitative coronary angiography (QCA) data at the target lesion(s) will be summarized overall, by treatment group, and for the difference between treatment groups using descriptive statistics, as per the table mockups. The variables to be summarized are listed in the sections below.

4.3.1 SYNTAX Score

• SYNTAX score at baseline.

4.3.2 Morphology

Pre-procedure (all subjects):

- Target Lesion Vessel (CASS Site Location)
- Thrombus
- Aneurysm
- Calcification
- Eccentric Lesion
- Lesion Angulation > 45°
- American College of Cardiology/American Heart Association (ACC/AHA) Lesion Class

Post-procedure (PCI arm only):

- Thrombus
- Aneurysm
- Dissection

4.3.3 Quantitative Coronary Angiography

Note that for the variables listed below, the reference vessel diameter (RVD) will be calculated using the user-defined method and percent diameter stenosis will be calculated using the interpolated method.

Pre-procedure (all subjects):

- Reference Vessel Diameter (RVD, in mm)
- Lesion Length (mm)
- Minimal Lumen Diameter (MLD, in mm)
- Percent Diameter Stenosis (%DS)

Post-procedure (PCI arm only):

- Reference Vessel Diameter (RVD, in mm)
- Minimal Lumen Diameter (MLD, in mm, In-Stent, In-Segment, Proximal, and Distal
- Percent Diameter Stenosis (%DS), In-Stent, In-Segment, Proximal, and Distal

4.4 SAFETY ANALYSIS

Adverse event and treatment results will be summarized for the ITT population only. AEs will be summarized by severity and relatedness. Serious AEs will be presented in a listing.

5 Changes From Protocol

At the request of the FDA reviewer, the As Treated (AT) analysis set is added for the analysis of the primary and secondary powered endpoints.

For consistency purposes, for the 30-day time-point, the primary endpoint will be measured as a KM estimate (as it is being done for all other time-points), and not as a rate. As such, it will be analyzed with the same methods as this endpoint is analyzed at the other time-points.

6 **REFERENCES**

- (3) Hintze J. NCSS and PASS. Number Cruncher Statistical Systems. Kaysville, Utah. 2005.
- (4) Sianos, Georgios et al., The SYNTAX Score: an angiographic tool grading the complexity of coronary artery disease. EuroInterv.2005;1:219-227.
- (5) SAS/STAT User's Guide, Version 9.1, SAS Publishing, 2004.
- (7) Farooq V, et al., Anatomical and clinical characteristics to guide decision making between coronary artery bypass surgery and percutaneous coronary intervention for individual patients: development and validation of SYNTAX score II. Lancet. 2013. 381, 639-50.
- (8) Pocock SJ, et al., The win ratio: a new approach to the analysis of composite endpoints in clinical trials based on clinical priorities. European Heart Journal, 2012. 33, 176-182.
- (9) Tong BC, et al., Weighting Composite Endpoints in Clinical Trials: Essential Evidence for the Heart Team. Ann Thorac Surg, 2012. 94, 1908-1913.
- (10) Finkelstein D.M. and Schoenfeld D.A., Combining mortality and longitudinal measures in clinical trials. Statistics in Medicine, 1999; 18(11): 1341-1354.

7 APPENDICES

APPENDIX A: Planned Analyses for IFU

In addition to the pre-specified hypotheses testing on the primary and major secondary endpoints, descriptive analysis regarding the components of the primary and major secondary endpoints will be provided for the ITT population. Moreover, the primary and major secondary endpoint, along with their components will be provided for the following subsets of subjects:

- **Diabetics**
- Female
- Elderly (age ≥ 65 years)
- Number of diseased vessels (with ≥ 2 diseased vessels)
- Bifurcation in LM

All subgroups are defined based on information related to the index procedure. If a subgroup is defined by lesion level characteristics, then in general, the subgroup is restricted to single lesion treated subjects and subjects with staged procedure(s) will be excluded.

The following Quality of Life (QOL) scores/scales collected at baseline, 1 month, 6

months, 12 months, and 3 years will be summarized using mean and standard deviation:

- Seattle Angina Questionnaire (SAQ)
- London School of Hygiene Dyspnea Questionnaire
- Medical Outcomes Study 12-item Short Form Health Status questionnaire (SF-12)
- Patient Health Questionnaire (PHQ-8)
- EuroQol (EQ-5D)

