7.3.1. General Considerations

• **Procedural "staging"** in PCI subjects is defined as a planned elective second PCI procedure at a separate setting to optimally complete the PCI. Given the complexity of the ULMCA subjects randomized in this clinical trial, it is anticipated that a substantial proportion of PCI subjects may fall into the category of staged procedures. The criteria for staging are left to the operator's best judgment, and there is expected variability among operators and sites. In general, the decision to stage is based on the overall extent and complexity of coronary

disease, the case complexity (intra-procedure difficulty encountered by the operator), the duration of the procedure, assessment of radiation exposure, the total volume of contrast utilized, the clinical stability of the subject, and other subject-related factors (diabetes, renal function, etc.). The recommended timing of a planned elective staged second PCI procedure is optimally within 2 weeks post index procedure, but in all subjects it is strongly recommended that it be completed within 4 weeks post index procedure.

The reason(s) for the staged procedure must be documented in the eCRF and source documents. Furthermore, the need for staging, and all specific lesions planned to be treated during the staged procedure should be declared beforehand in the eCRF at the time of initial baseline procedure.

Unless otherwise planned, stented segment(s) treated during the initial baseline procedure

should not be treated again during the staged procedure. If the e-CRF from the first procedure did not indicate that such re-intervention was planned, the re-PCI will be considered to be clinically indicated, and will be analyzed as an event (although not necessarily ischemia-related – the Clinical Events Committee will make this determination).

Only randomized study stents should be used during staged procedures, if possible. During a staged procedure the same study assessments (such as ECG and cardiac biomarker collection) apply as during the baseline procedure. All subjects must be taking the protocol required post ULMCA medications (such as aspirin and ADP antagonists) prior to staged procedure. The staged procedures will not affect the original follow-up schedule.

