7.5. Completeness of Revascularization

All ischemic myocardial areas, such as those subtended by coronary arteries with visually assessed \geq 50% diameter stenosis, should be revascularized.

For subjects randomized to PCI: In prior PCI vs. CABG trials, the determination of and execution of "completeness of revascularization" strategy has been an important consideration. In this trial, the philosophical approach is to perform PCI of all significant ischemia-producing lesions as opposed to all lesions which appear to be significant by angiographic visual assessment, especially if the angiographic lesions are 40-70% diameter stenosis. Moreover, it is strongly recommended that PCI is performed only in ischemia-producing lesions, in most cases not treating non ischemia-producing lesions. Ischemia-producing lesions are defined as those which (1) are \geq 70% angiographic diameter stenosis (visually assessed), or if <70% diameter stenosis, are either (2a) associated with noninvasive functional evidence of ischemia in the territory of the lesion (not explained by another coronary stenosis), and/or (2b) intra-procedure FFR \leq 0.80 (note FFR procedure guidelines), and/or (2c) IVUS minimal luminal area \leq 4.0 mm² (for non left main lesions) with plaque burden >60% (note IVUS procedure guidelines).

For subjects randomized to CABG: Since all subjects in this study have important ULMCA stenosis, according to contemporary surgical standards, all subjects should have at least one bypass graft to the left anterior descending coronary artery system and a second graft to circumflex coronary artery system. All coronary arteries with \geq 50% stenosis and \geq 1.5 mm in diameter should be revascularized.

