9.1.4. Subgroup Analyses

Subgroup analysis will be performed in the intent-to-treat population. However, these comparisons are not powered for hypothesis testing, and the analysis results are considered exploratory. The proposed subgroups are listed in Section 21.2.

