16.1.4. Definition of Coronary Revascularization Procedures

A coronary revascularization procedure may be either a coronary artery bypass graft (CABG) surgery or a percutaneous coronary intervention (PCI) (for example, angioplasty, stenting), regardless of procedural success.

Coronary revascularization procedures may be further classified as follows:

- Urgent: an urgent procedure is one that is performed within 48 hours of upon diagnosis of the subject's status due to urgency of the medical condition, but is not otherwise considered emergent
- Emergent: an emergent procedure is one that is performed as soon as possible (usually within 6 hours)
- Elective: an elective procedure is one that is scheduled and is not urgent or emergent

Procedural Success may be defined as follows:

• CABG: the successful placement of at least one conduit with either a proximal and distal anastomosis or a distal anastomosis only

• PCI: successful balloon inflation with or without stenting and the achievement of a residual stenosis <50% of the left anterior descending coronary artery and/or the left circumflex artery. The balloon inflation and/or stenting could have been preceded by adjunctive device use (e.g., Angiojet, rotational atherectomy etc.)

Target Lesion: A lesion revascularized in the index procedure (or during a planned or provisional staged procedure). The LM target lesion extends from the left main stem ostium to the end of the 5 mm proximal segments of the left anterior descending and left circumflex arteries as well as the ramus intermedius if the latter vessel has a vessel diameter of ≥ 2 mm.

Target Vessel: The target vessel is defined as the entire major coronary vessel proximal and distal to the target lesion including upstream and downstream branches and the target lesion itself. The left main and any vessel originating from the left main coronary artery or its major branches is, by definition, considered a target vessel for the purposes of this trial (unless either the LAD or LCX are occluded at baseline and no attempt was made to revascularize these territories by either PCI or CABG).

Target Vessel-Non-Target Lesion: The target vessel but non-target lesion consists of a lesion in the epicardial vessel/branch/graft that contains the target lesion; however, this lesion is outside of the target lesion by at least 5 mm distal or proximal to the target lesion determined by quantitative coronary angiography (QCA)

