2.4.1 Intent-to-Treat Population

The ITT population will consist of all subjects randomized in the study, regardless of the treatment actually received. Subjects will be analyzed in the treatment group to which they were randomized, regardless of actual treatment received.

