3 ANALYSIS CONSIDERATIONS

3.1 GENERAL STATISTICAL METHODS

Baseline demographic, clinical, angiographic, procedural and device data, and treatment results will be summarized using descriptive summary statistics. All data collected will be summarized overall and by treatment arms.

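### The SAP's single-lesion, non-staged restriction for labelling subgroups would, if applied to left main bifurcation, select the two arms differently and undo the randomized comparison

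*SAP*

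**What the plan says.** SAP Appendix A plans descriptive results on the primary and major secondary endpoints and their components, for the IFU, in five subsets: diabetics, women, age 65 or over, two or more diseased vessels, and bifurcation in the left main. It then sets two rules. First, "All subgroups are defined based on information related to the index procedure". The second concerns any subset that rests on "lesion level characteristics, then in general, the subgroup is restricted to single lesion treated subjects and subjects with staged procedure(s) will be excluded". It labels none of the five as lesion-level and does not say when the general rule gives way.

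Other text bears on this:

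- Protocol 7.3.1: staging in PCI subjects "is defined as a planned elective second PCI procedure at a separate setting to optimally complete the PCI". It is left to the operator and expected in a substantial proportion of PCI subjects; no percentage is given.
- Protocol 7.5: PCI should treat ischemia-producing lesions. Every CABG subject should have "at least one bypass graft to the left anterior descending coronary artery system and a second graft to circumflex coronary artery system", and all arteries of at least 1.5 mm with at least 50% stenosis should be revascularized.
- Protocol 9.1.4: "Subgroup analysis will be performed in the intent-to-treat population". SAP 2.4.1 defines that population: "Subjects will be analyzed in the treatment group to which they were randomized, regardless of actual treatment received".
- SAP 3.1: "All data collected will be summarized overall and by treatment arms".
- SAP 3.5 lists distal left main bifurcation involvement, yes or no by core lab, with no single-lesion or staging restriction.

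**The concern.** A subgroup comparison in a randomized trial is protected only if membership does not depend on what happened after assignment. How many lesions were treated, and whether the procedure was staged, are both decided after assignment and by different rules in each arm. Among the reasons protocol 7.3.1 gives for staging are extent and complexity of disease, difficulty during the procedure, clinical stability, diabetes and renal function. These are plausibly related to risk, so removing staged subjects could remove higher-risk subjects from one arm only.

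The subset may be large: in the single-arm left main study of the XIENCE V stent described in protocol 2.7.2, 74% of lesions were bifurcations. Because SAP 3.5 reports nearly the same anatomy without exclusions, two different PCI and CABG results could exist for largely the same patients, with the restricted one intended for labelling.

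**Working it through.** **Which subsets the rule can reach.** Diabetes, sex and age are subject-level. Number of diseased vessels is a vessel- or subject-level count, and a single-lesion restriction would largely empty the subset with two or more. Left main bifurcation is what remains.

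**How each filter acts by arm.**

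1. *Staging.* Protocol 7.3.1 defines it only as a second PCI procedure. Under ITT the exclusion falls almost entirely on the PCI arm, apart from CABG-assigned subjects who were treated by PCI.
2. *Single lesion treated.* No counting rule exists for CABG. If lesions are counted by territory grafted, the expected LAD and circumflex grafts could exclude nearly every CABG subject. If the left main complex counts as one lesion, few may be excluded.

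**Whether the restriction is needed to classify subjects.** It is not. Protocol 16.1.4 treats the left main as one target lesion: "The LM target lesion extends from the left main stem ostium to the end of the 5 mm proximal segments" of the LAD and circumflex (and the ramus, if large enough). Bifurcation status can be assigned whatever other lesions are treated or staged.

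**Size, as an illustration only.** Appendix A states no figure to reproduce. Inputs:

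- True 3-year risk of 11% in both arms: the planning rate in SAP 2.5.1, assumed to hold in the subset.
- s, the share of an arm excluded. For staging alone, 10 to 20% is assumed. For both rules in PCI, 46% is used: the multivessel share in the protocol 2.7.2 study, as a proxy. For CABG, 0, 46% and 80% are assumed.
- r, the risk in excluded subjects relative to those kept: 1.5 to 2, assumed.

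Kept risk = 11% / (1 - s + s × r). With r = 1 this is 11% for any s, so the shift is 0.

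Staging alone, CABG unrestricted at 11.00%:

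| PCI excluded | r | PCI kept risk | PCI minus CABG |
|---|---|---|---|
| 10% | 1.5 | 11/1.05 = 10.48% | -0.52 |
| 10% | 2 | 11/1.10 = 10.00% | -1.00 |
| 20% | 1.5 | 11/1.10 = 10.00% | -1.00 |
| 20% | 2 | 11/1.20 = 9.17% | -1.83 |

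Both rules, PCI excluded 46%: kept risk is 11/1.23 = 8.94% (r = 1.5) or 11/1.46 = 7.53% (r = 2).

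| CABG excluded | CABG kept risk, r = 1.5 / r = 2 | PCI minus CABG, r = 1.5 / r = 2 |
|---|---|---|
| 0% | 11.00 / 11.00% | -2.06 / -3.47 |
| 46% | 8.94 / 7.53% | 0 / 0 |
| 80% | 11/1.40 = 7.86% / 11/1.80 = 6.11% | +1.09 / +1.42 |

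**Precision, even with balanced exclusion.** Taking 74% of 950 gives 703 per arm; keeping 54% leaves about 380. The 95% half-width for the difference is 1.96 × sqrt(2 × 0.11 × 0.89 / n): 3.27 points at n = 703 and 4.45 points at n = 380.

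**The case against.** The sentence is doubly conditional, and Appendix A never calls left main bifurcation lesion-level. SAP 3.5 handles the near-equivalent factor as a subject attribute, and the single-unit definition in protocol 16.1.4 supports that reading. On it, the sentence is unclear or unused rather than harmful. This stands as a limit: the documents establish the ambiguity, not that the rule will be applied. But no other listed subset would plausibly trigger it.

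A PCI versus CABG display is also inferred. Appendix A specifies no difference, interval or test, and the by-arm layout comes from general text. SAP section 4 lets table mock-ups override the layout, and those were not available here. A side-by-side table is expected rather than certain, and columns shown together will be compared even without a p-value.

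The illustration rests on weak proxies. The staging share and risk ratios have no source. The 46% is multivessel disease, not multiple lesions treated, and the 74% is a share of lesions; both come from a 174-subject cohort in which 76.2% had SYNTAX scores of 0-32, whereas this trial excludes scores of 33 or more. The numbers therefore show only that the shift is unpredictable and need not be negligible. They are not evidence of a particular bias.

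Finally, an unrestricted comparative analysis already exists in SAP 3.5. That limits the damage, but it is also the reason the restriction is unnecessary.

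**Conclusion.** The concern holds, in conditional form. Appendix A does not say which subsets its lesion-level rule governs. If it is applied to left main bifurcation, the by-arm summary is not a randomized comparison and does not fit the ITT population that protocol 9.1.4 sets for subgroup analysis.

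The direction is unknown because the CABG lesion count is undefined. The illustrated shifts run from about -3.5 to +1.4 points and vanish if excluded subjects carry no extra risk; they depend on the assumed risk ratios and exclusion shares. Some precision is lost whatever the direction.

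The consequence is confined to one descriptive IFU summary. The primary and powered secondary ITT tests, the SAP 3.5 subgroup analysis and the other IFU subsets are unaffected. The change should be made, but it does not threaten the trial's main conclusions.

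**What to change.** In SAP Appendix A, define the left main bifurcation subset from baseline core-lab data in all ITT subjects, matching SAP 3.5, and drop the single-lesion and staging restriction from any PCI and CABG summary. If restricted lesion-level results are wanted for the device label, show them for the PCI arm only, in a supplementary table labelled as such. If the sentence is kept for any subset, name that subset and state how treated lesions are counted in CABG subjects.

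The cost is SAP wording only. The core-lab variable is already planned for SAP 3.5, so no new data are needed.
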